### 1.3 Deferoxamine

Deferoxamine (DFO) was the first commercially available iron chelator, which was approved in 1968 for the treatment of acute iron intoxication and of chronic iron overload due to transfusion-dependent anemias. To be effective, DFO must be delivered as a constant infusion, usually subcutaneously, for 8 to 12 hours a night, at least five days per week at recommended doses of 20-60 mg/kg/day. Deferoxamine chelates iron by forming a stable complex that prevents the iron from entering into further chemical reactions. It readily chelates iron from ferritin and hemosiderin but not readily from transferrin; it does not combine with the iron from cytochromes and hemoglobin. Long-term use of DFO is associated with stabilization or decline in all three measures of iron load and with

decreased iron-induced morbidity and with improved survival of transfusion-dependent thalassemia patients ([Borgna-Pignatti C et al. 2004](#); [Kwiatkowski JL. 2008](#)).

However, there are some important adverse reactions to deferoxamine. These include local skin reactions which are almost universal, and auditory and visual disturbances. There is a susceptibility to certain gram-negative infections, in particular *Yersinia enterocolitica*, in patients who receive deferoxamine.

## 2 OBJECTIVES

### 2.1 Primary Objective

To determine the efficacy of deferiprone vs. deferoxamine in the treatment of iron overload in patients with sickle cell disease or other anemias.

### 2.2 Secondary Objectives

The secondary objectives are:

- To evaluate the effect of deferiprone vs. deferoxamine on the patients' quality of life;
- To evaluate the safety and tolerability of deferiprone vs. deferoxamine.

### **3 INVESTIGATIONAL PLAN**

#### **3.1 Overall Study Design**

This study is a 52-week, prospective, multi-center, two-arm, randomized, open-label, parallel design of deferiprone therapy vs. deferoxamine. The study will consist of a Baseline Phase and a Treatment Phase. Three hundred (300) male and female patients with sickle cell disease (SCD) or other anemias requiring blood transfusion will be enrolled.

#### **3.2 Discussion of Study Design**

This study has been designed to evaluate the efficacy, safety, and tolerability of deferiprone vs. deferoxamine in patients with SCD or other anemias requiring iron chelation. Patients will participate in a Baseline Phase followed by a Treatment Phase.

Excluded from the study will be patients with thalassemia syndromes, myelodysplastic syndrome (MDS), myelofibrosis, Diamond Blackfan anemia and primary bone marrow failure.

##### **Baseline Phase:**

During the Baseline Phase, patients who sign an informed consent/assent form will undergo initial screening. On the final day of the Baseline Phase, patients' eligibility will be determined, based on inclusion/exclusion criteria, and qualified patients will enter the Treatment Phase.

##### **Treatment Phase:**

At the beginning of the Treatment Phase, patients will be randomized in a 2:1 ratio to receive (1) deferiprone or (2) deferoxamine. The Treatment Phase will be 52 weeks in duration. At the end of the 52 weeks of treatment, patients will be invited to enter a 2-year extension phase.

##### **Deferiprone treatment arm:**

During the study, patients will be prescribed Ferriprox 500 mg tablets or deferiprone 80 mg/mL oral solution, according to patient preference or product's availability, for administration three times a day (tid). The dose of deferiprone will be based on the transfusional iron input and the severity of iron load at baseline, and may be adjusted on the basis of the magnitude of change in iron overload during the study.

##### **Deferiprone 25 mg/kg tid:**

Patients with transfusional iron input  $\leq 0.3$  mg/kg/day in the 3 months prior to baseline

##### **AND**

Patients with a baseline measure of iron load of:

- Serum ferritin  $<2500$   $\mu$ g/L

**AND**

- LIC <15 mg/g dry weight

**AND**

- Cardiac T2\* > 20 ms

**Deferiprone 33 mg/kg tid:**

Patients with a transfusional iron input > 0.3 mg/kg/day in the 3 months prior to baseline

**OR**

Patients with at least one baseline measure of iron load as follows:

- Serum ferritin  $\geq$ 2500  $\mu$ g/L

**OR**

- LIC  $\geq$ 15 mg/g dry weight

**OR**

- Cardiac T2\*  $\leq$  20 ms

Dosing of all patients will be initially at 15 mg/kg tid for 1 week, which will be increased to 20 mg/kg tid in Week 2 and to 25 mg/kg tid in Week 3, which will be the treatment dose for the remainder of the trial, unless a patient meets the 33 mg/kg tid dosing criteria. In that case, the dose of deferiprone will be increased further to 33 mg/kg tid in Week 4, and this dose will be the treatment dose for the remainder of the trial.

The dose of deferiprone will also be increased to 33 mg/kg tid at any time during the trial if the mean daily transfusional iron input increases to more than 0.3 mg/kg body weight for at least 3 consecutive months OR at Week 26 if there is less than 10% improvement from baseline to Week 26 in at least one of the measures indicative of iron overload (serum ferritin, cardiac MRI T2\* or LIC).

Dose reduction recommendations will be based on regular assessment of safety markers for adverse reactions that are possibly dose dependent, such as gastrointestinal upset, increases in serum liver enzyme levels, and arthropathies.

**Deferoxamine treatment arm:**

During the study, patients will be prescribed deferoxamine as per the approved US prescribing information at doses of 20 – 40 mg/kg/day for children (<16 years of age) and 40–50 mg/kg/day in adults ( $\geq$ 16 years of age) as 8 – 12 h subcutaneous infusion for 5 – 7 days per week. The dose of deferoxamine will be based on the transfusional iron input, on the severity of iron load at baseline, and on the magnitude of its change during the study.

Deferoxamine 20 mg/kg/day (children) or 40 mg/kg/day (adults):

Patients with transfusional iron input  $\leq 0.3$  mg/kg/day in the 3 months prior to baseline

**AND**

Patients with a baseline measure of iron load of:

- Serum ferritin  $<2500$   $\mu$ g/L \*

**AND**

- LIC  $<15$  mg/g dry weight

**AND**

- Cardiac T2\*  $> 20$  ms

- \* If there is a delay in obtaining the results of the baseline serum ferritin assessment from the central laboratory, the most recent result (obtained within the last 3 months) should be used to calculate the starting DFO dosage. This dosage must remain in effect until the baseline serum ferritin results become available, at which time it is to be adjusted if necessary. If no serum ferritin measure has been obtained within the last 3 months, the start of dosing must be deferred until the baseline results are available.

Deferoxamine up to 40 mg/kg/day (children) or 50 mg/kg/day (adults):

Patients with a transfusional iron input  $> 0.3$  mg/kg/day in the 3 months prior to baseline

**OR**

Patients with at least one baseline measure of iron load as follows:

- Serum ferritin  $\geq 2500$   $\mu$ g/L

**OR**

- LIC  $\geq 15$  mg/g dry weight

**OR**

- Cardiac T2\*  $\leq 20$  ms

*Children (<16 years of age)*

The dose of deferoxamine will also be increased up to 40 mg/kg for 5 – 7 days per week at any time during the trial if the mean daily transfusional iron input increases to more than 0.3 mg/kg body weight for at least 3 consecutive months OR at Week 26 if there is less than 10% improvement from baseline to Week 26 in at least one of the measures of iron overload (serum ferritin, cardiac MRI T2\* or LIC).

*Adults ( $\geq 16$  years of age)*

The dose of deferoxamine will be increased up to 50 mg/kg for 5 – 7 days per week at any time during the trial if the mean daily transfusional iron input increases to more than 0.3 mg/kg body weight for at least 3 consecutive months OR at Week 26 if there is less

than 10% improvement from baseline to Week 26 in at least one of the measures of iron overload (serum ferritin, cardiac MRI T2\* or LIC).

Dose reduction recommendations will be based on regular assessment of safety markers.

Efficacy, safety and tolerability evaluations will occur according to the schedule of evaluation (Appendix 18.1). Rescue medication (intravenous administration of deferoxamine or combination of 2 iron chelators: deferiprone, deferoxamine or deferasirox) for the treatment of iron overload will not be allowed during the Treatment Phase. Should iron overload symptoms become intolerable for the patient despite dose adjustment, the Investigator should withdraw the patient from the study.

If a patient withdraws early, he or she will return to the clinic for an Early Termination Visit as soon as possible, and no later than 1 month following treatment discontinuation. All of the efficacy and safety evaluations will be performed at the last study visit or the Early Termination visit, whichever comes first.

### **3.3 Study Sites and Study Duration**

Study sites will be located in but not limited to countries in North America, Europe, and the Middle East. While the goal will be to keep the number of sites to a minimum, it is expected that the study will engage sites worldwide due to the anticipated difficulty in enrolling patients with a 33% probability of being allocated to the deferoxamine treatment arm.

Each patient is expected to participate in the study for approximately 60 weeks (from the Screening Visit to the End of Study Visit).

## **4 STUDY POPULATION**

### **4.1 Number of Patients**

Three hundred (300) male and female patients with SCD disease or other anemias requiring blood transfusion will be enrolled in the study. Excluded from the study will be patients with thalassemia syndromes, MDS, myelofibrosis, Diamond Blackfan anemia, and primary bone marrow failure. At least 80% of the enrolled patients will have sickle cell disease.

Patients who withdraw from the study after starting study medication will not be replaced.

### **4.2 Inclusion Criteria**

Patients will be included in the study only if they meet **all** of the following criteria:

1. Male or female  $\geq$  2 years of age;
2. Have sickle cell disease (confirmed by Hb electrophoresis or more specific tests) or other conditions with iron overload from repeated blood transfusions (see exclusion criteria for exceptions);

3. Baseline LIC >7 mg/g dw (measured by MRI);
4. Patients who have received no less than 20 transfusions of RBCs;
5. Patients who have received at least 1 transfusion per year in the last 2 years and who are expected to have a continuing requirement (based on Investigator's judgement) during the duration of the trial;
6. Patients, and when applicable their legal representatives, will provide a signed and dated written assent/informed consent prior to the first study intervention; patients will be able to adhere to study restrictions, appointments and evaluation schedule.
7. Female patients of childbearing potential must have a negative pregnancy test result at Screening and Baseline Visits. In addition, a female patient of childbearing age who is sexually active must confirm that during the study and for 30 days following the completion of the study or early termination she:
  - will use an effective method of contraception, OR
  - has had a tubal ligation (supporting evidence required), OR
  - has had a hysterectomy (supporting evidence required), OR
  - participates in a non-heterosexual lifestyle, OR
  - indicates her only male sexual partner has been sterilized (supporting evidence required).

Effective methods of contraception include oral contraceptives, intrauterine devices (IUDs) or condom, providing it is used with contraceptive foam or cream, or abstinence from sexual intercourse. Supporting evidence for sterilization consists of a surgical report or letter from the family physician;

8. If the patient is a heterosexual sexually-active fertile male, patient must confirm, in writing, that he and/or his female partner will use an effective method of contraception for the length of the trial and for 30 days following completion of the study or early termination. Effective methods of contraception for males include condoms or sterilization or abstinence from sexual intercourse.

### 4.3 Exclusion Criteria

Patients will be excluded from the study for **any** of the following reasons:

1. Thalassemia syndromes;
2. Myelodysplastic syndrome (MDS) or myelofibrosis;
3. Diamond Blackfan anemia;
4. Primary bone marrow failure;

5. Patients with a baseline LIC >30 mg/g dw (measured by MRI);
6. Unable or unwilling to undergo a 7-day washout period if currently being treated with deferiprone or deferoxamine or deferasirox;
7. Previous discontinuation of treatment with deferiprone or deferoxamine due to adverse events;
8. History or presence of hypersensitivity or idiosyncratic reaction to deferiprone or deferoxamine;
9. Treated with hydroxyurea within 30 days;
10. History of malignancy;
11. Evidence of abnormal liver function (serum ALT level(s) > 5 times upper limit of normal at screening or creatinine levels >2 times upper limit of normal at screening);
12. A serious, unstable illness, as judged by the Investigator, during the past 3 months before screening/baseline visit including but not limited to: hepatic, renal, gastro-enterologic, respiratory, cardiovascular, endocrinologic, neurologic or immunologic disease.
13. Clinically significant abnormal 12-lead ECG findings;
14. Cardiac MRI T2\* <10 ms
15. Myocardial infarction, cardiac arrest or cardiac failure within 1 year before screening/baseline visit;
16. Bowel disease causing malabsorption;
17. HIV positive patient;
18. Unable to undergo MRI;
19. Presence of metallic objects such as artificial joints, inner ear (cochlear) implants, brain aneurysm clips, pacemakers, and metallic foreign bodies in the eye or other body areas that would prevent use of MRI imaging;
20. History of alcohol or drug abuse;
21. Treatment with an investigational drug within 30 days or 5 half-lives (whichever is longer) preceding the first dose of study medication;
22. Participation in another clinical trial during the conduct of this study;
23. Pregnant, nursing females and females of childbearing potential who are sexually active and unwilling, or unable, to use an acceptable method of contraception;
24. Mental incapacity, unwillingness or language barriers precluding adequate understanding or co-operation;
25. Any condition that, in the opinion of the Investigators, would adversely affect ability to complete the study or its assessments.

## 4.4 Enrolment Violations

The criteria for enrolment must be followed explicitly. If there is inadvertent enrolment of patients who do not meet enrolment criteria, such patients should be withdrawn from the study.

## 4.5 Withdrawal Criteria

A patient has the right to withdraw from the study at any time and for any reason without consequence to future care by the Investigator or study center. The reason for withdrawal will be sought.

When a patient decides to withdraw from the study, he/she should always be contacted, not only to determine the reason(s) for withdrawing, but also to determine if there were any adverse events (AEs). Whenever possible, the patient should return for a clinic visit at the time of or soon after discontinuation of study medication but no later than 1 month after treatment discontinuation. All investigational products and materials should be returned. If any AEs occurred, the Investigator must attempt to follow up with the outcome for 30 days post-study withdrawal.

Data collected for patients who are withdrawn after receiving the study drug should be evaluated for efficacy and safety.

If, for any reason, the Investigator decides to withdraw a patient before completing the study, the reason for withdrawal must be entered into the source document and the electronic case report form (eCRF).

A patient may be withdrawn from the study at any time for any of the following reasons:

- Patient request;
- Medical reasons considered significant by the patient and/or Investigator;
- Requirement for concomitant medication that may interfere with the evaluation of study medication, or may be contraindicated;
- Occurrence of other illnesses that affect the patient's further participation in the study or evaluation of study medication;
- Significant changes in QTcF interval (defined as QTcF change of greater than 60 ms) are detected;
- Any other situation where, in the opinion of the Investigator, continuation of the study would not be in the best interest of the patient.

A patient **must** be withdrawn from the study if any of the following conditions apply:

- Pregnant or planning to become pregnant (see [Section 9.2](#) Procedures in Case of Pregnancy);
- Occurrence of any adverse reaction characterized as life-threatening or disabling;

- Non-compliance with blood counts. During the first 6 months, if a patient misses a weekly ANC monitoring visit, then missing a further 3 of the next 5 visits (i.e., a total of 4 out of 6) will result in automatic withdrawal. During the last 6 months, ANC monitoring will be done biweekly, and missing 3 consecutive biweekly blood counts will result in automatic withdrawal.
- Termination of the study by the Sponsor;
- Patient experiences severe neutropenia/ agranulocytosis (refer to [Section 8.2.4.9](#) for definition and management).

## 4.6 Treatment Interruptions

Study medication will be interrupted for **ANY** of the following reasons:

- If the patient develops an infection during the study, deferiprone must be interrupted immediately and neutrophil count should be obtained and monitored more frequently (every 2 days if ANC  $<1.5 \times 10^9/L$ ). Patients should be advised to report immediately to their physician any symptoms indicative of infection such as fever, sore throat, and flu-like symptoms. They will be provided with a thermometer, and instructed to seek immediate medical attention at a hospital or clinic if they experience fever (temperature  $>38.0^{\circ}C/100.4^{\circ}F$ ). Body temperature may be measured at the mouth, axilla, or ear. Patients/legal guardians will be provided with an emergency services card with contact information, and will be advised to carry this card at all times. In presence of confirmed fever and/or infection, patients will be required to have their neutrophil counts tested as soon as possible and no later than 24 hours after the symptoms of infection are detected. Therapy with deferiprone can be re-initiated once all symptoms have been resolved and it is deemed safe by the Investigator.
- If temperature is  $>38.0^{\circ}C/100.4^{\circ}F$  and ANC is  $\leq 0.5 \times 10^9/L$ , the following must be done:
  - Commence therapy with antibiotics immediately (treatment should depend on the site of the suspected infection and on local antibiotic policy)
  - Perform a chest x-ray, and collect blood and other relevant cultures (if possible, collect culture samples before initiating antibiotics)
- If the patient develops moderate neutropenia while on deferiprone (refer to [Section 8.2.4.9](#) for definition), therapy must be interrupted immediately and neutrophil count must be obtained and monitored every 2 days. Therapy with deferiprone can be re-initiated once two successive ANCs are  $>1.5 \times 10^9/L$  and it is deemed safe by the Investigator. The patient will be withdrawn from the study if the ANC remains  $<1.5 \times 10^9/L$  by the end of a two-week period (14 days) ([Section 8.2.4.9](#)).

## 4.7 Pregnancy

All female participants of childbearing potential will be administered a serum and urine pregnancy test prior to starting study medication. A negative test result will be required prior to study entry. Patients of childbearing potential should not become pregnant during the study and therefore must agree to use an approved method of contraception (as

defined in Appendix 18.2) for 30 days prior to Day 1 (at least 3 months for hormonal contraceptives), throughout the course of the trial, and for 30 days following early termination or the last visit.

In the situation where a female patient is withdrawn prematurely from the study because of a pregnancy, study medication must be stopped immediately, the Sponsor must be informed immediately via the Pregnancy Report Form, and the patient must be closely followed up during her pregnancy, as much as possible. Update reports must be provided to the ApoPharma Medical Safety department at mid-pregnancy and at delivery or at termination of the pregnancy.

Male patients must inform the Investigator if their female partner becomes pregnant during the trial or within one month after trial completion.

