## **18.2 Acceptable Methods of Contraception and Definitions Related to Childbearing Potential**

1. Approved methods of contraception will consist of the following for the purposes of this study or must follow local requirements:

- Oral contraceptive medications with condom or spermicide
- Hormonal implants with condom or spermicide
- Injectable contraceptive medications with condom or spermicide
- Condom used with spermicide.

If the hormonal contraception is used, it should have a Pearl index <1%.

2. Women who are not able to bear children and therefore do not need to practice a medically accepted method of contraception will include those who:

- Have had a tubal ligation
- Are post-menopausal (i.e. last menstrual period was more than 2 years ago)
- Have had an hysterectomy or oophorectomy
- Participate in a non-heterosexual lifestyle,
- Have a male sexual partner has been sterilized (supporting evidence required).

3. Patients who are peri-menopausal (i.e., less than 2 years since their last menstrual period), must have a pregnancy test and must use one of the medically accepted methods listed above (under point 1) if they wish to participate in the study.

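### Appendix 18.2 can class fertile women as unable to bear children, and footnote 3 and inclusion 7 do not fully match section 4.7 and Appendix 18.2 on contraception (minor, safety only)

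*Protocol*

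**What the plan says.** **Testing.** Protocol section 4.7 states: "All female participants of childbearing potential will be administered a serum and urine pregnancy test prior to starting study medication". The visit lists in section 5 and the schedule in Appendix 18.1 use the same restriction to females of childbearing potential.

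**Definition.** Only Appendix 18.2 sets out who falls outside that group. Item 2 introduces "Women who are not able to bear children and therefore do not need to practice a medically accepted method of contraception". Its list contains tubal ligation, post-menopause, and hysterectomy or oophorectomy (not limited to bilateral). It also contains "Participate in a non-heterosexual lifestyle" and "Have a male sexual partner has been sterilized (supporting evidence required". Item 3 says that peri-menopausal women "must have a pregnancy test and must use one of the medically accepted methods listed above".

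**Lead time.** Section 4.7 requires an approved method, "defined in Appendix 18.2) for 30 days prior to Day 1 (at least 3 months for hormonal contraceptives". Footnote 3 in Protocol 18.1, repeated in SAP Table 1, asks for at least one month on an approved method and makes no separate mention of hormonal methods.

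**Methods.** Appendix 18.2 item 1 begins: "Approved methods of contraception will consist of the following for the purposes of this study or must follow local requirements". The list has oral, implanted and injectable hormonal methods, each paired with a condom or spermicide (the first entry is "Oral contraceptive medications with condom or spermicide"), and condom with spermicide. Inclusion 7 in section 4.2 gives a different set: oral contraceptives, IUD, condom with foam or cream, and abstinence. It does not refer to 18.2.

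**The concern.** A site can follow one current part of the protocol and arrive at a different practice from a site that follows another.

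- **Who is tested.** A non-heterosexual lifestyle or a sterilised partner does not make a woman infertile, and a woman with one remaining ovary may be fertile. If a site reads item 2 as the definition of who lacks childbearing potential, these women drop out of testing as well as contraception.
- **When contraception starts.** A site working from the schedule of events sees one month and no hormonal rule.
- **Which methods count.** A site working from the inclusion criteria may accept a method that is not on the 18.2 list.

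The stake is participant safety. Section 9.2 requires deferiprone to be stopped and the patient withdrawn if she becomes pregnant. Without testing, a pregnancy may be recognised later. The analysis is not touched.

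**Working it through.** The plan has no statistical figure to reproduce here. The check is a comparison of texts, with two small counts.

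**1. Who is tested**

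- Section 4.7 requires patients of childbearing potential to use an approved method and states no exemption. Under that sentence, the item 2 waiver works only if the listed women are outside childbearing potential. That same step would take them out of testing.
- Item 3 asks for a test by name; item 2 does not mention testing. The contrast invites the same reading.
- Inclusion 7 points the other way. It first asks for negative tests at Screening and Baseline, and then, as a further condition, offers lifestyle or partner sterilisation as alternatives to contraception. It requires the sterilised man to be the woman's only male partner, a limit that 18.2 drops.
- Inclusion 7 does not settle the matter. Its alternatives also include tubal ligation and hysterectomy, and it moves from childbearing potential to childbearing age. Being on its list does not prove that a woman is tested.

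Outer bound on missed tests (section 8.2.2):

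- Serum at entry: screening/baseline and baseline = 2.
- Serum on treatment: Weeks 4, 8, 12, 16, 20, 26, 32, 36, 40, 44, 48 and 52 = 12.
- New enrolee: 2 + 12 = 14 serum, plus 1 urine at baseline.
- Woman already on treatment: 14 − 2 = 12 serum at most, and no urine test.

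**2. Lead time for a hormonal method**

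- Three consecutive calendar months last 89 days (28 + 31 + 30) to 92 days (31 + 31 + 30).
- Screening opens at Day −60 (section 5.2). A method started then has run 60 days by Day 0 and 61 by Day 1.
- Shortfall if started at Day −60: 89 − 61 = 28 to 92 − 60 = 32 days.
- Shortfall at the footnote's one-month floor: three months less one, which is two calendar months, 59 (31 + 28) to 62 (31 + 31) days.
- No shortfall if she started 3 months ahead.

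The case is narrow. A woman using both condom and spermicide with her hormonal method already has a listed non-hormonal method, for which 30 days is enough. The gap concerns, for example, an oral contraceptive with spermicide only.

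**3. Methods**

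| Method | Inclusion 7 | 18.2 list |
|---|---|---|
| Oral contraceptive with condom or spermicide | accepted | listed |
| Oral contraceptive alone | accepted* | not listed |
| IUD | accepted | not listed |
| Abstinence | accepted | not listed |

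*Assumes that the foam-or-cream proviso in inclusion 7 applies only to the condom, which is the natural reading.

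Three options therefore differ, unless local requirements admit them.

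**The case against.** The strongest reply is that the texts can be reconciled.

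- **Testing.** Item 2 waives contraception and nothing more. Inclusion 7 waives it for the lifestyle and partner groups too. The women concerned are at low risk, partner sterilisation needs supporting evidence, counselling of sexually active patients continues whatever the definition, and section 9.2 obliges a patient to report a pregnancy or a plan for one.
- **Lead time.** Footnote 3 is a minimum and section 4.7 is stricter. A site that follows 4.7 satisfies both.
- **Methods.** Section 4.7 makes 18.2 the definition, and 18.2 admits local requirements. The contraception clause of inclusion 7 and exclusion 23 both concern sexually active women, so the absence of abstinence from the list matters little there.
- **Reach.** According to the SAP's sample size text, enrolment is on hold with 17 patients ongoing.

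Most of this stands, and it is why the point is minor. It does not remove the point. The label in item 2 is inaccurate for some women, and the tests depend on the term that 18.2 defines. The schedule is a working document for sites and omits a rule that it should carry. Inclusion 7 gives no sign that another list governs. Under SAP section 3.7, enrolment may restart on the DSMB's advice, and on-treatment testing and methods also bear on any women among the 17.

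**Conclusion.** The inconsistency is real, minor and confined to participant safety. It has no effect on alpha, power or the estimate.

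**Size.** The outer bound is 14 serum tests and 1 urine test missed for a new enrolee, or at most 12 serum for a woman already on treatment. A hormonal lead time could fall short by 28 to 32 days if the method is started at Day −60, and by 59 to 62 days at the footnote's floor. Three contraceptive options are treated differently. The documents do not show how many women any of this touches. For women who are tested, negative results before dosing and monthly serum tests limit the second and third points.

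**Assumptions.** The figures assume a site that takes 18.2 item 2 as its definition for testing, or that works from footnote 3 without 4.7. Months are calendar months.

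**What does not follow.** A reader might infer that the protocol instructs sites not to test fertile women; it does not, because item 2 is silent on testing and inclusion 7 can be read as keeping them tested. A reader might also see a contradiction between footnote 3 and section 4.7; the footnote is an incomplete minimum, and 4.7 should control. Nor do the documents show that any woman went untested or entered early.

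**What to change.** 1. **Appendix 18.2 item 2.** Keep only tubal ligation, post-menopause, hysterectomy and bilateral oophorectomy.
2. **New item in 18.2.** List non-heterosexual lifestyle, sterilisation of the woman's only male partner (supporting evidence required) and abstinence, under the wording *exempt from contraception; pregnancy testing still required*. Section 4.7 has no exemption of its own, so the item should say that it applies there too.
3. **Footnote 3, in Protocol 18.1 and SAP Table 1.** Add the 3-month minimum for hormonal methods from section 4.7.
4. **Inclusion 7 and exclusion 23.** Refer to *a method approved under Appendix 18.2, including its local-requirements clause*, so that locally admitted methods are not lost.

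Whether to add the IUD to the 18.2 list is a clinical choice for the sponsor.

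**Cost.** The wording can go into the next protocol amendment, which under section 14.6 needs IRB/IEC approval and regulatory notification or approval before use. The SAP needs one matching footnote. There would be a few extra pregnancy tests, within the bounds above. Some women would need re-counselling: those relying on an IUD or an oral contraceptive alone where local requirements do not admit it, and any woman until now exempted on the basis of a unilateral oophorectomy.
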